5.2 Data Analysis

5.2.1 Quantitative data analysis

The sensitivity, specificity and predictive values of the NICE ultra-brief depression screening questions and the EPDS will be calculated at 20 weeks of pregnancy and 3-4 months post-birth with two-by-two contingency tables against the ICD-10 diagnostic gold standard. Associated 95% confidence intervals will also be calculated for each estimate at each time point. Receiver Operating Characteristic (ROC) curves will also be constructed to determine performance characteristics for each depression measure. Based on the predictive properties of the depression screening measures, optimum times for screening will be identified. The numbers of women with indeterminate and/or missing results (if available). The baseline characteristics of women with indeterminate and/or missing results (if available). The baseline characteristics of women with indeterminate and/or missing results will be compared to those who have complete data using descriptive statistics. A logistic regression model will also be used to identify predictors of non-response.

McNemars test will be used to explore the temporal stability of responses between 20 weeks of pregnancy and 3-4 months post-birth for each of the depression screening measures. The co-existence of depressive symptoms alongside other common mental health problems will be summarised descriptively (mean, standard deviation, median, minimum and maximum and frequency and percentages at established cut points) at each time-point.

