- 2. Longitudinal Assessment: To judge the temporal stability of positive and negative screens between pre- and post-birth, and to ascertain whether there is an optimum time to screen for perinatal depression.

- 3. Standardised Diagnostic Assessment of Co-Morbidity: To examine the co-existence of depressive symptoms alongside common mental health problems.
- 4. Evaluation of Acceptability: To determine the acceptability (to expectant and new mothers and healthcare professions) of the NICE ultra-brief depression screening questions and the EPDS during the perinatal period, and the potential implications for the care pathway.
- Estimation of Cost-Effectiveness: To assess the cost-effectiveness of the NICE ultra-brief depression screening questions against the EPDS for routine screening for perinatal depression in maternity services.

4 Methods

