The two depression screening tools - the NICE ultra-brief depression screening questions and the EPDS - will be validated against a WHO (World Health Organisation) diagnostic gold standard clinical assessment of depression (International Classification of Disease, ICD-10) at two stages - 20 weeks pregnancy and 3-4 months post-birth. By cross-validating the diagnostic gold standard against scores on the two depression screening tools at these two time points in the perinatal care pathway we will be able to assess the diagnostic accuracy of these tools in terms of false positives, false negatives and true negative results. This in turn will yield measures of sensitivity, specificity and positive and negative likelihood ratios (with 95% confidence intervals) and hence the diagnostic utility of the depression screening tools. This validation method will also permit us to judge the temporal stability of positive and negative screens between pre- and post-birth and the natural history of screen-positive depression across the perinatal period. This will also enable us to ascertain the persistence of early screens in predicting longer-term problems. This will provide important information on the nature of the relationship between depression before and after birth.

A diagnostic assessment of co-morbidity will be made in two ways: by using previously validated questionnaires and by using the WHO diagnostic gold standard structured interview to ascertain the presence of common mental health problems, such as anxiety disorders and somatoform complaints (physical symptoms with a lower probability of physical pathology). An assessment of psychological co-morbidity will be made at three time points during pregnancy and early motherhood: 20 weeks pregnancy, 3-4 months post-birth and 1 year post-birth. This will allow us to examine the co-existence of depressive symptoms alongside other common mental health problems during the perinatal period. This will inform the delivery of psychosocial treatments by mental health practitioners to take account of other common mental health problems, such as anxiety and somatic complaints.

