5.1 Sample size calculation

We will aim to recruit 379 pregnant women. This sample size calculation is based on a previously developed method (43), for an expected sensitivity of 95% and a minimal acceptable lower 95% confidence interval (CI) of more than 0.80 with 0.95 probability, where estimated prevalence of prenatal and postnatal depression is 20%. Attrition is estimated at 34% based on a previous pilot validation study of the NICE ultra-brief depression screening questions to identify perinatal depression in a limited perinatal population (17).

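### The plan undertakes to identify optimum screening times from separate stage-specific estimates that include prevalence-dependent predictive values, with no between-stage comparison of accuracy

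*Protocol*

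**What the plan says.** Objective 2 (protocol section 3) is partly "to ascertain whether there is an optimum time to screen for perinatal depression". Section 5.2.1 sets out the analysis that serves it. "The sensitivity, specificity and predictive values of the NICE ultra-brief depression screening questions and the EPDS will be calculated at 20 weeks of pregnancy", and again at 3-4 months post-birth, each with a 95% confidence interval. "Receiver Operating Characteristic (ROC) curves will also be constructed to determine performance characteristics for each depression measure". The timing conclusion then follows in one sentence: "Based on the predictive properties of the depression screening measures, optimum times for screening will be identified".

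The section does not say which property decides or how the two stages are to be compared. McNemar's test is planned across the stages, but on the screening responses and not on their accuracy against the CIS-R. Section 4.1.2 adds likelihood ratios with 95% confidence intervals, which section 5.2.1 does not take up. It also says that the persistence of early screens as predictors of later problems will be examined.

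The sample size section uses one prevalence for both stages ("where estimated prevalence of prenatal and postnatal depression is 20" per cent) and allows for loss: "Attrition is estimated at 34% based on a previous pilot validation study". Section 5.2.1 plans a descriptive comparison of women with and without complete data and a logistic model for non-response. It does not link either to the timing question.

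**The concern.** PPV and NPV depend on prevalence as well as on the test. If they help to decide when to screen, a stage can appear better only because more or fewer women were depressed at that stage, or because depressed women were more or less likely to stay in the study. The protocol contains routes to such a shift: the expected loss, the rule in section 4.6 that women who do not answer the letter sent after a fetal loss are not contacted again, and the procedure in Appendix 3 for women whom the CIS-R identifies as depressed or anxious, which can include notifying their GP.

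The wording adds to this. The objective asks whether there is an optimum time, but the analysis section says that optimum times will be identified. Two separate sets of estimates will almost always differ somewhat. Without an interval for the difference, nothing separates a real advantage from noise. The study is intended to inform NICE guidance and national screening policy, so a timing statement is likely to be used.

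**Working it through.** **Inputs.** Recruitment target 379, expected sensitivity 95%, prevalence 20% at both stages and attrition 34% (section 5.1). Pilot figures for the NICE questions: sensitivity 100% at both stages, specificity 68% antenatal and 65% postnatal. EPDS: sensitivity 91% and specificity 91% (all section 4.4). Prevalences other than 20% and the unequal retention rates below are assumptions.

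**Stage sizes.** With an exact one-sided 95% lower limit, 50 cases give probability 0.962 that the limit exceeds 0.80 when sensitivity is 0.95. Then 50/0.20 = 250, and 250/0.66 = 378.8, rounded up to 379. The target is reproduced. If all the attrition has occurred by 3-4 months, the stages have about 379 and 250 women.

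**Prevalence, with the test held constant.** PPV = se·p / [se·p + (1 − sp)(1 − p)], at se 0.95 and sp 0.68:

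- p = 0.20: 0.190/(0.190 + 0.256) = 0.426
- p = 0.15: 0.1425/(0.1425 + 0.272) = 0.344
- p = 0.10: 0.095/(0.095 + 0.288) = 0.248

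For the EPDS at 0.91/0.91, PPV is 0.717 at 20% and 0.641 at 15%. NPV = sp(1 − p) / [sp(1 − p) + (1 − se)p] moves the other way. For the NICE questions it is 0.544/0.554 = 0.982 at 20% and 0.578/0.5855 = 0.987 at 15%. The same data could therefore favour one stage on PPV and the other on NPV.

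**Difference expected from accuracy.** At se 0.95 and p = 0.20, moving specificity from 0.68 to 0.65 gives 0.190/(0.190 + 0.280) = 0.404, against 0.426. With the pilot sensitivity of 100%, the values are 0.200/0.456 = 0.439 antenatal and 0.200/0.480 = 0.417 postnatal. Either way the gap is about 2 points. On the pilot figures, a postnatal prevalence above about 21.5% reverses the order, although postnatal specificity is lower.

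**Selective loss alone.** Keep 50% of cases and 70% of non-cases (assumed): 0.20 × 0.50 = 0.10 and 0.80 × 0.70 = 0.56, a total of 0.66, which matches the planned retention. Stage 2 prevalence becomes 0.10/0.66 = 15.2%, and EPDS PPV falls from 0.717 to 0.644. Equal retention changes nothing.

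**Chance alone.** Take 20% prevalence and 0.95/0.68 at both stages. The screen-positive fraction is 0.446, so about 169 women screen positive at stage 1 and 111.5 at stage 2. The SE of the PPV difference is √[0.426 × 0.574 × (1/169 + 1/111.5)] = 0.060, so the 95% range is ±0.118. A simulation of 200,000 runs gives the same range, and about ±0.14 for the EPDS. If prevalence falls from 20% to 15% with accuracy unchanged, stage 1 has the higher PPV in about 91% of runs (NICE questions) and 82% (EPDS). These figures treat the stages as independent, an approximation because the same women are followed.

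**What a comparison of accuracy could resolve.** On the same approximation there are about 76 cases and 303 non-cases at stage 1, and 50 and 200 at stage 2. For sensitivity 0.95 at both stages, the half-width for the difference is 1.96 × √(0.0475/75.8 + 0.0475/50) = 0.078. For specificities 0.68 and 0.65 it is 1.96 × √(0.2176/303.2 + 0.2275/200) = 0.084. A 3-point difference in specificity, as in the pilot, would not be separated from zero.

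**The case against.** Four points can be made for the protocol, and each limits the finding.

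- A reader might infer that PPV or NPV alone will pick the time. The text does not say so. The sentence follows sensitivity, specificity, predictive values and ROC curves, and section 4.1.2 adds likelihood ratios. The criterion is undefined, and predictive values are among the candidates.
- A reader might infer that the two stages compare different women. They do not. Section 4.4 collects data from all women at each time point, so stage 2 is the retained part of one cohort and differs in composition only through attrition. The planned non-response analysis would help to reveal this.
- A reader might infer that the study cannot show whether a 20-week screen finds women who are depressed later. Section 4.1.2 states that aim, and the CIS-R is given at all three stages. Only the table that would deliver it is not named.
- A true change in prevalence is a legitimate part of deciding when to screen, because it alters yield and false positives. It misleads only when read as better test performance or when selective loss produced it.

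It can also be said that the choice of method belongs in an analysis plan, which is not at hand. That holds for the model. It does not hold for the rule itself: the protocol fixes both the basis of the choice and the wording of the conclusion, and that wording goes further than its own objective.

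**Conclusion.** The point stands as a weakness in a stated rule for half of Objective 2. Followed as written, section 5.2.1 allows a stage to be named the better time to screen because of a prevalence shift, selective loss or chance. An assumed fall in prevalence from 20% to 15% moves PPV by about 8 points for an unchanged test at 0.95/0.68, against about 2 points from the pilot difference in specificity. Chance alone covers about 12 points either way.

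The documents do not support saying that the artefact will occur. The protocol assumes 20% at both stages, 15% is an illustration, and the pattern of loss is unknown. The sizes also assume that all the attrition falls before 3-4 months and that the stages are independent. The main accuracy estimates at each stage are not affected.

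**What to change.** In section 5.2.1, replace the timing sentence as follows.

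1. Base the comparison on between-stage differences in sensitivity, specificity and likelihood ratios, with 95% CIs that allow for the same women being measured twice (for example GEE or a bootstrap clustered on the woman). Name the deciding measure in advance.
2. Use women assessed at both stages as the main set or as a sensitivity set. Sensitivity and specificity do not move with prevalence by arithmetic, but selective loss can still change the case mix.
3. Report predictive values as secondary, at the observed and at common prevalences, so that a change in prevalence is shown separately from test performance.
4. Tabulate the 20-week screen against CIS-R depression at 3-4 months and 1 year, to deliver the persistence aim of section 4.1.2.
5. Word the question as whether either stage is better, and claim no optimum if the CI for the difference includes zero (one, for a ratio of likelihood ratios).

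No new data are needed. The cost is a little more analysis and a smaller paired set. With half-widths of about 8 points for sensitivity and specificity, the study may well be unable to name a better stage, and the plan should allow for that answer.

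### With 34% attrition expected, section 5.2.1 plans a non-response model but states no use of it in the 3-4 month estimates

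*Protocol*

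**What the plan says.** - **Sample size (5.1).** The target is stated as "We will aim to recruit 379 pregnant women". Loss is allowed for: "Attrition is estimated at 34% based on a previous pilot validation study". The protocol does not say at which stage these women are lost or whether loss is related to depression.
- **Accuracy (5.2.1).** Sensitivity, specificity and predictive values "will be calculated at 20 weeks of pregnancy and 3-4 months post-birth with two-by-two contingency tables against the ICD-10 diagnostic gold standard". The same section uses the predictive properties of the screening measures to identify the best times to screen.
- **Stability (5.2.1).** McNemar's test is applied to each screening measure at 20 weeks and 3-4 months.
- **Missing results (5.2.1).** The baseline characteristics of women with indeterminate or missing results "will be compared to those who have complete data using descriptive statistics", and "A logistic regression model will also be used to identify predictors of non-response". No weighting, imputation or sensitivity analysis is stated.
- **Aims.** Sections 2, 3 and 4.1.2 include the stability of screens across birth, the persistence of early screens and the natural history of screen-positive depression.

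**The concern.** Two-by-two tables and McNemar's test count only women with both results. Without a stated adjustment, the 3-4 month estimates therefore describe the women who stayed. Dividing by the retention rate protects the number of women analysed, but not how well they represent those recruited.

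If depressed women are lost more often, postnatal prevalence and positive predictive value read too low. Persistence can also read too low. Loss after the first interview leaves the 20-week figures alone, so the two time points are affected unequally. Objective 2 asks when to screen, and a difference in predictive values produced by dropout could be read as a difference between times. Section 5.2.1 already plans the model that would address part of this, but stops at identifying predictors.

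**Working it through.** **The plan's own figure.** The criterion is "for an expected sensitivity of 95% and a minimal acceptable lower 95% confidence interval (CI) of more than 0.80 with 0.95 probability". Using an exact one-sided 95% lower limit, the smallest number of cases that meets it is 50 (probability 0.962). At 20% prevalence, 50/0.20 = 250 women. Allowing for 34% loss, 250/0.66 = 378.8, so 379. The figure reproduces.

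**Inputs for the illustrations.**
- From the documents: prevalence 20% at both stages, overall retention 66% and NICE-question sensitivity 0.95 (5.1); postnatal specificity 0.65 and EPDS 0.91/0.91 (4.4).
- Assumed: persistence 50%, the retention splits, and test accuracy that depends only on current status. New cases among women not depressed at 20 weeks follow as (0.20 − 0.20×0.50)/0.80 = 12.5%.

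**No bias.** With 66% retained in every group, prevalence is 20%. NICE-question PPV = 0.20×0.95/(0.20×0.95 + 0.80×0.35) = 0.19/0.47 = 0.404. EPDS PPV = 0.182/(0.182 + 0.072) = 0.717.

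**A. Loss depends on 20-week status (retention 50% depressed, 70% others).**
- Overall retention: 0.20×0.50 + 0.80×0.70 = 0.66, matching 5.1.
- Share of retained women depressed at 20 weeks: 0.10/0.66 = 15.2%.
- Observed 3-4 month prevalence: 0.152×0.50 + 0.848×0.125 = 18.2%.
- NICE-question PPV: 0.182×0.95/(0.182×0.95 + 0.818×0.35) = 0.376. EPDS PPV: 0.692.
- Persistence is taken among women depressed at 20 weeks, who share one retention rate, so it stays at 50%.
- Weighting by 20-week status restores the 20:80 mix: 0.20×0.50 + 0.80×0.125 = 20%, and PPV returns to 0.404.

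**B. Loss depends on 3-4 month status (the same 50% v 70%).**
- Observed prevalence: 0.20×0.50/0.66 = 15.2%. NICE-question PPV 0.326; EPDS PPV 0.644.
- Observed persistence: 0.50×0.50/(0.50×0.50 + 0.50×0.70) = 41.7%.
- Observed new cases: 0.125×0.50/(0.125×0.50 + 0.875×0.70) = 9.26%.
- Weighting by 20-week CIS-R status gives 0.20×0.417 + 0.80×0.0926 = 15.7%. Persistence stays at 41.7%. Weighting on that variable barely helps here.
- Depression among the missing is 0.20×0.50/0.34 = 29.4%, so the odds ratio, missing v retained, is (0.294/0.706)/(0.152/0.848) = 2.33. A sensitivity analysis that includes this value recovers the truth.

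**Sensitivity and specificity.** They are unchanged in A and B. If retention instead depends on the same-stage screen (0.50 positive, 0.80 negative), sensitivity reads 0.95×0.50/(0.95×0.50 + 0.05×0.80) = 0.92 and specificity 0.65×0.80/(0.65×0.80 + 0.35×0.50) = 0.75. Predictive values are then not biased.

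**The case against.** The strongest reply is that weighting, imputation and missing-data sensitivity analyses are usual analysis-plan content, and the analysis plan is not at hand. Nothing in 5.2.1 is false or contradictory, and its sentences on missing results are visibly broken in the available text. This stands in part: the lack of such detail alone would not be a point. But 5.2.1 does address missing results, chooses its steps and stops at description, while naming estimators that need both results.

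Several stronger readings are tempting and should be resisted:
- *That the protocol fixes a complete-case rule.* It does not say so. Reliance on women with both results follows from the named methods and the absence of a stated adjustment.
- *That bias is shown.* Only the overall 34% is given. Every split above is an assumption, and equal loss gives no bias.
- *That the planned model would cure it.* Illustration B shows otherwise when loss follows later depression.
- *That biased predictive values enter the decision model.* Section 5.2.3 bases it on sensitivity and specificity. Section 2 mentions natural history as a gap in the existing model, but not predictive values.
- *That 1-year accuracy is affected.* Validation is planned only at 20 weeks and 3-4 months.

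Section 4.1.1 also plans to set the results against self-report data from the whole BABY cohort. That gives some outside check on representativeness, but is not an adjustment.

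**Conclusion.** The point holds as a modest, inexpensive improvement. As written, the protocol describes non-response but does not carry the model into the 3-4 month estimates. Prevalence, predictive values and persistence at that stage can be biased if loss is related to depression. The comparison of screening times is exposed, taking the predictive properties in 5.2.1 to include predictive values.

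Under illustration A the effect is about 2 percentage points of prevalence and 0.03 of NICE-question PPV, and it is correctable. Under B it is about 5 points of prevalence, 8 points of persistence and 0.08 of PPV, and weighting on 20-week CIS-R status leaves nearly all of the prevalence error and all of the persistence error. Both rest on the assumed retention of 50% v 70%. The 20-week estimates are not touched by later loss, and sensitivity and specificity are not touched by loss that depends only on true current status.

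**What to change.** In 5.2.1 (or in the analysis plan, with a sentence in 5.2.1 pointing to it):

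1. Use the planned non-response model, with stage 1 CIS-R status, NICE questions, EPDS, PHQ-9, GAD-7, site and age, to form inverse-probability weights, or use multiple imputation with the same variables.
2. Report 3-4 month prevalence, predictive values, accuracy and pre-/post-birth persistence this way, beside the figures from women with both results.
3. Add one sensitivity analysis over a range of higher odds of depression in missing women, starting at 1 and extending past 2.33. It covers what stage 1 data cannot correct: loss driven by depression that arises or persists after stage 1.

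No new data collection is needed. Section 4.4 allows telephone and postal collection to be combined, so some stage 1 measures may be missing and the model should allow for that. The cost is slightly wider intervals and a little more analysis.

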The need for good prospective epidemiological estimates of perinatal depression and psychological co-morbidity has been identified in the most recent policy recommendation issued by the UK NSC (14). The natural history of depression during the perinatal period is under-researched with postnatal depression having received considerably more attention than prenatal depression. The finding that less than 50% of cases of perinatal depression are recognised is largely drawn from cross-sectional studies of postnatal depression. Consequently, we do not know the degree to which prenatal depression sufferers continue to be symptomatic in the postnatal period and what numbers of women with postnatal depression are 'new cases'. The BABY PaNDA study will allow us to examine the relationship between depression before and after birth.

Epidemiological research shows that depression commonly co-exists with other common mental health disorders such as general anxiety and somatoform complaints. This is important since assessments of depression without the recognition of co-existing psychological symptoms will lead to suboptimal treatment strategies. There is an increasing need for psychosocial interventions that address the range of co-morbid symptoms that are present and the rational use of such interventions should be informed by epidemiological estimates of need. Recent NICE guidance (18) has highlighted the importance of psychological co-morbidity. However, the issue of co-morbidity is not well understood in perinatal mental health research. The BABY PaNDA study seeks to address this knowledge gap by using a structured gold standard diagnostic interview to capture the full range of common mental health disorders.

Our previous research has shown that there are limited studies into the acceptability of routine screening and case-finding for postnatal depression (15, 19). If depression screening questions are to be used in routine clinical practice, then they should be acceptable to both expectant and new mothers and to healthcare professionals. Our research will therefore inform the implementation of the NICE-endorsed screening strategy based on expectant and new mothers' and healthcare professionals' acceptability of the depression screening tools and assessment of potential implications for the care pathway for women diagnosed with perinatal depression.

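### McNemar's test, the only analysis named for temporal stability, compares overall screen-positive rates and does not show whether individual women keep the same result

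*Protocol*

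**What the plan says.** Objective 2 in section 3 (Research Objectives) has two parts: "To judge the temporal stability of positive and negative screens between pre- and post-birth, and to ascertain whether there is an optimum time to screen". The text around it shows that the interest lies in individual women. Section 2 (Background) states that "we do not know the degree to which prenatal depression sufferers continue to be symptomatic in the postnatal period", and adds that the number of postnatal cases that are new is also unknown. Section 4.1.2 says of the repeated screening and interviews: "This will also enable us to ascertain the persistence of early screens in predicting longer-term problems".

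Section 5.2.1 gives the stability part one method, applied to each screening tool: "McNemars test will be used to explore the temporal stability of responses between 20 weeks of pregnancy and 3-4 months post-birth". The optimum-time part has its own sentence: "Based on the predictive properties of the depression screening measures, optimum times for screening will be identified". The protocol names no agreement measure, no kappa and no proportion of women staying positive or staying negative. It attaches no significance level or decision rule to the McNemar test.

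**The concern.** Stability of a screen within women is a property of the whole paired table: how many early positives remain positive, and how many early negatives remain negative. McNemar's test discards both concordant cells. Its null hypothesis is that the positive rate is the same at the two stages.

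Two errors of reading follow. If many women switch but in equal numbers each way, the test is non-significant and the screen may be called stable. If almost nobody switches but the few who do go the same way, the test can be significant and the screen may be called unstable. At stake is the answer to half of a numbered objective, and the persistence and new-case question raised in section 2, to which the named test gives no estimate.

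**Working it through.** **Inputs**
- Recruitment target 379, prevalence 20% before and after birth, attrition 34% (section 5.1).
- Pilot accuracy of the two questions: sensitivity 100% at both stages, specificity 68% antenatally and 65% postnatally (section 4.4).
- Assumed: the joint cells of each table, 250 complete pairs, a two-sided 0.05 level (the protocol states none).

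**The plan's own figure.** Section 5.1 sets the target: "We will aim to recruit 379 pregnant women". It is calculated "for an expected sensitivity of 95% and a minimal acceptable lower 95% confidence interval (CI) of more than 0.80 with 0.95 probability". Using an exact one-sided 95% lower limit, the smallest number of cases meeting this is 50. Then 50 / 0.20 = 250 women, and 250 / 0.66 = 378.8, so 379. The target is reproduced, and 250 is a fair number of pairs for illustration.

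**Expected screen-positive totals.** Positive rate = prevalence × sensitivity + (1 − prevalence) × (1 − specificity).
- 20 weeks: 0.20 × 1.00 + 0.80 × 0.32 = 0.456, or 114 of 250.
- 3-4 months: 0.20 × 1.00 + 0.80 × 0.35 = 0.480, or 120 of 250.

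**Formulas.** Let a = positive at both stages, b = positive then negative, c = negative then positive, d = negative at both.
- Exact McNemar p = 2 × P(X ≤ min(b, c)), with X binomial (b + c, 0.5), capped at 1.
- Agreement = (a + d) / 250.
- Kappa = (agreement − chance) / (1 − chance). For these totals, chance = (114 × 120 + 136 × 130) / 250² = 0.502.

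**Same totals, opposite stability**

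| | a / b / c / d | Exact p | Agreement | Kappa | Early positives staying positive |
|---|---|---|---|---|---|
| No individual stability (a = 114 × 120 / 250 ≈ 55) | 55 / 59 / 65 / 71 | 0.65 | 50.4% | 0.00 | 55/114 = 48% |
| Maximum stability | 114 / 0 / 6 / 130 | 2 × 0.5⁶ = 0.031 | 97.6% | 0.95 | 114/114 = 100% |

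**Why the direction reverses.** With the totals fixed, b − c is always −6, so the uncorrected chi-square is 36 / (b + c). It is 36 / 124 = 0.29 in the first row and 36 / 6 = 6.0 in the second. The more women change their result, the smaller the statistic.

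**Other totals (assumed)**
- 20% positive at both stages: 10/40/40/160 and 45/5/5/195 both give p = 1.00, with kappa 0.00 and 0.875.
- 20% then 23.6% positive: 49/1/10/190 gives p = 2 × (1 + 11) / 2¹¹ = 0.012, with agreement 95.6% and kappa 0.87.

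**The case against.** The best defence is that the protocol uses the test to explore stability, sets no threshold and never says that a p-value will be turned into a declaration of stable or unstable. A shift in the overall positive rate is one legitimate group-level meaning of stability, and a significant result reflects a real net change. The paired table needed for the test already holds the four cells, and an analysis plan that is not shown may report them. All of this is fair, and it limits the consequence. It does not remove the defect: the protocol ties this one test to the stability question, while sections 2 and 4.1.2 frame the question by woman. An analysis plan that follows section 5.2.1 would inherit the mismatch.

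It can also be said that zero association within the same woman is extreme. That is true, and with totals of 114 and 120 the exact test falls below 0.05 only at maximum stability (b = 1, c = 7 already gives 2 × (1 + 8) / 2⁸ = 0.070). But the statistic falls with every additional pair of opposite switches, so the reversal does not depend on the extreme cases. The 49/1/10/190 table shows a significant result without perfect retention.

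A reader might infer more than the protocol supports:
- **That all of Objective 2 fails.** The optimum-time part is planned separately, from predictive properties.
- **That the missing 1-year analysis is an error.** Objective 2 speaks of before and after birth, and section 5.2.1 matches the two validation stages. Section 4.1.2 does look to longer-term problems, but an analysis of that could sit in the analysis plan.
- **That the decision model loses required inputs.** Section 4.1.4 takes screening performance, quality of life and resource use from this study, and section 5.2.3 runs on sensitivity, specificity and the four diagnosis groups. Only section 2 points towards temporal stability, as a limit of the earlier model.

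**Conclusion.** The point holds for the stability half of Objective 2. The test named in section 5.2.1 answers whether the positive rate changed, not whether women kept their result. With the protocol's own expected positive rates, it is non-significant at kappa 0.00 (p = 0.65) and significant at kappa 0.95 (p = 0.031). With equal rates it cannot tell kappa 0.00 from 0.875 (p = 1.00 for both).

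The positive totals come from the protocol's figures; the joint cells, the 250 complete pairs and the 0.05 level are assumptions. The property of the test does not depend on them. It would be too strong to say that the study will reach a false conclusion, since the protocol does not commit to reading the p-value as a measure of stability. Sensitivity, specificity, predictive values and the sample size are not affected.

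**What to change.** In section 5.2.1, make the paired 20-week by 3-4-month table the stability analysis for each screening tool. From it report, each with a 95% confidence interval:
- the proportion still positive among women positive at 20 weeks, a / (a + b);
- the proportion still negative among women negative at 20 weeks, d / (c + d), and its complement, the newly positive, c / (c + d).

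Add percent agreement and kappa. Give the same table for CIS-R depression, since section 2 asks about persistence and new cases of depression itself and not only of screens. Keep McNemar's test, described only as a test of change in the overall positive rate.

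The planned numbers give usable precision. With 114 early positives, the widest approximate 95% half-width is 1.96 × √(0.25 / 114) = 9 percentage points. With 50 CIS-R cases (20% of 250) it is 1.96 × √(0.25 / 50) = 14 points.

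The cost is a change of wording and a few extra tables, with no new data or recruitment. Further analyses, such as intraclass correlation or mean change for the EPDS total, go beyond what this defect requires.
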